5.2 Eligibility: As per inclusion and exclusion criteria mentioned below-

5.2.1 Inclusion criteria:

Patients with severe COVID-19 will be considered for randomization and will be transfused convalescent plasma within 3 days of symptom onset (Severe COVID-19) Severe COVID -19 defined by WHO Interim Guidance and the Guideline of Diagnosis and Treatment of COVID-19 of National Health Commission of China (version 5.0) along with confirmation by real-time RT-PCR assay with severe disease i.e. meeting any 2 of the following criteria-

1. Patients on ventilator (in last 24 hours)
2. Respiratory distress, RR \geq 30 beats/min
3. Oxygen saturation level less than 90 % in resting state
4. Partial pressure of oxygen (PaO₂)/oxygen concentration (FiO₂) \leq 300 mmHg
5. Lung infiltrates > 50% within 24 to 48 hours

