- c. hospital admission for non-invasive ventilation or high-flow oxygen therapy=4;
- d. hospital admission for oxygen therapy (but not requiring high-flow or non-invasive ventilation) =3;
- e. hospital admission but not requiring oxygen therapy=2;
- f. discharged or having reached discharge criteria (defined as clinical recovery-ie, normalization of pyrexia, respiratory rate 94% on room air, and relief of cough, all maintained for at least 72 h) =1.

2.2.2 Secondary objectives:

1. Proportion of patients in each category according to the ordinal scale
[Time Frame: 48 hours]
2. Proportion of patients in each category according to the ordinal scale [Time Frame: 7 day]
3. Proportion of patients in each category according to the ordinal scale
[Time Frame: Day 14]
4. Proportion of patients in each category according to the ordinal scale
[Time Frame: Day 28]
5. Duration of oxygen therapy in both groups [Time Frame: Day 28]
6. Duration of hospital stay in both groups [Time Frame: Day 28]
7. Proportion of patients on mechanical ventilation at day 7 in both groups
[Time Frame: Day 7]
8. Mortality in both groups [Time Frame: Day 7]
9. Mortality in both groups [Time Frame: Day 28]

10. Duration of Intensive Care Unit stay [Time Frame: Day 28]
11. Incidence of adverse effects in both groups [Time Frame: Day 28]
12. Presence of antibodies against SARS-CoV-2 in serum after plasma administration
[Time Frame: Day 0] (IgG Titres against S1, RBD antigen, and SARS CoV2
neutralizing antibody titres)
13. Presence of antibodies against SARS-CoV-2 in serum after plasma administration
[Time Frame: Day 7] (IgG Titres against S1, RBD antigen, and SARS CoV2
neutralizing antibody titres)
14. Change in Cytokines in both groups
15. Change in acute phase reactants in both groups

Section 3: Study Methods

3.1 Trial design: It will be a open-labeled; phase III randomized controlled trial.

3.2 Randomization: The randomization will be done by using stratified block randomization method into two treatment groups. The allocation concealment will be done by using “Sequentially Numbered Opaque Sealed Envelopes” (SNOSE) method.

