5.3 Recruitment: Consort flow will include as per protocol-

Patients will be assessed for eligibility >>>randomization will be done for eligible participants >>> Allocation of treatment in two groups (one arm will be given convalescent plasma with standard medical treatment and another arm will be given standard medical treatment only) >>> follow up till 28 days.

5.4 Withdrawal/ Follow-up: Withdrawal is not expected, follow up till 28 days in all enrolled patient.

5.5 Baseline patient characteristics: following variables will be considered:

- Age at screening (years) = date of screening.
- Time from initial admission to randomization(days) = date of transfusion allotment by snooze method and transfusion of plasma.
- O₂ saturation at baseline.
- PiO₂/FiO₂ ratio at baseline.
- Respiratory rate at baseline.
- Need of Mechanical ventilation at baseline.
- SOFA score at baseline.
- For those who died: Date of death – transfusion start date or date of randomization.
- For those who are alive: Date of last follow-up – transfusion start date or date of randomization.

Section 6:

Analysis

6.1 Outcome definitions:

6.1.1 Definition of primary endpoint: Time to clinical improvement (Clinical improvement: Reduction of two points in ordinal scale or live discharge from the intensive care unit, whichever is earlier)

6.1.2 Secondary endpoints:

1. The proportion of patients in each category according to the ordinal scale at 48 hours and day 7, 14, and 28 after randomization
2. Duration of oxygen therapy
3. Duration of hospital stay
4. The proportion of patients on mechanical ventilation at day 7. (after randomization)
5. Mortality at day 7 and day 28 (after randomization)
6. Duration of Intensive Care Unit stay
7. Incidence of adverse effects in both groups
8. Presence of antibodies against SARS-CoV-2 in serum after plasma administration.
9. Cytokines and acute phase reactants

6.2 Analysis methods:

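### A patient who enters at ordinal score 2 and stays on the ward cannot have the primary event, and the entry rule does not exclude such a patient

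*SAP*

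**What the plan says.** **Endpoint.** SAP 2.2.1 and 6.1.1 give the primary event as "Reduction of two points in ordinal scale or live discharge from the intensive care unit, whichever is earlier", followed to day 28. Neither section names the score from which the reduction is measured.

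**Scale.** SAP 2.2.1 sets six levels. The lowest, score 1, is "discharged or having reached discharge criteria". The next is "hospital admission but not requiring oxygen therapy=2". Scores 3 to 5 are levels of respiratory support, and 6 is death.

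**Entry.** SAP 5.2.1 requires severe, RT-PCR-confirmed disease, "meeting any 2 of the following criteria". The five are:
1. "Patients on ventilator (in last 24 hours")
2. respiratory distress with a rate of at least 30
3. "Oxygen saturation level less than 90 % in resting state"
4. PaO2/FiO2 of 300 mmHg or less
5. "Lung infiltrates > 50% within 24 to 48 hours"

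No criterion is mandatory. No minimum ordinal score, oxygen therapy or ICU admission is required.

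**Analysis set and baseline list.** SAP 4.3.2 keeps every randomised patient in the analysis. SAP 5.5 lists baseline saturation, PaO2/FiO2, respiratory rate, need for mechanical ventilation and SOFA, but not the ordinal score.

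**The concern.** The endpoint is a change of fixed size on a scale with a floor, so every patient needs room to make that change. From score 2 there is no such room. The only other route is leaving the ICU alive, which a patient who stays on the ward cannot do.

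For a score-2 ward entrant the endpoint then works the wrong way round. Steady recovery and discharge home is a non-event through day 28. Deterioration into the ICU followed by leaving it alive is an event. If plasma kept such a patient out of the ICU, it would also prevent the recorded improvement. A ward patient entering at score 3 and going home on the same day would count as a success.

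At stake is whether the recorded event means clinical improvement for every randomised patient, as the objective in 2.2.1 intends. Loss of power is a lesser matter.

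**Working it through.** **1. Room on the scale.** Largest possible fall = entry score − 1:

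| Entry score | Largest fall | Two-point fall possible? |
|---|---|---|
| 5 | 4 | yes |
| 4 | 3 | yes |
| 3 | 2 | yes |
| 2 | 1 | no |

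**2. Does the entry rule keep score 2 out?** Two of five criteria give 10 minimal qualifying pairs. Six omit the ventilator criterion: 2+3, 2+4, 2+5, 3+4, 3+5 and 4+5. Five of these six contain criterion 3 or 4, a measured oxygenation deficit. Only 2+5 (respiratory rate and infiltrates) contains neither ventilation nor such a deficit. Entry at score 2 is therefore open on the text, and this pair is the clearest route.

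**3. The SAP's sample size (3.3).** Medians of 24 and 18 days give a hazard ratio of 18/24 = 0.75 for standard treatment against plasma. With 1.96 and 0.84:
- per arm = 2 × (1.96 + 0.84)² / (ln 0.75)² = 189.5, so 190 per arm and 380 in total. This reproduces the stated figure.
- The formula as printed lacks the factor 2 and would give 94.7. The stated 190 includes it.

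**4. Effect on power.** Let q be the share of the 400 who enter at score 2 and never enter the ICU. The SAP does not give q; 2%, 5% and 10% are assumptions. These patients contribute no events. Power = Φ(ln(4/3) × √(events/4) − 1.96).

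*(a) The SAP's own basis, every other patient has an event:* events = 400 × (1 − q).

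*(b) 28-day follow-up with exponential times:* the day-28 event probabilities are 1 − 2^(−28/24) = 0.555 and 1 − 2^(−28/18) = 0.660. Expected events are 200 × (0.555 + 0.660) = 243 at q = 0, falling by 400 × q × 0.607.

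| q | Patients | (a) events | (a) power | (b) events lost | (b) events | (b) power |
|---|---|---|---|---|---|---|
| 0 | 0 | 400 | 82.0% | 0 | 242.9 | 61.1% |
| 2% | 8 | 392 | 81.3% | 4.9 | 238.0 | 60.2% |
| 5% | 20 | 380 | 80.1% | 12.1 | 230.7 | 58.9% |
| 10% | 40 | 360 | 77.9% | 24.3 | 218.6 | 56.6% |

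The step from 82.0% to 61.1% in the first row comes from follow-up ending at day 28. It is a separate matter and is not attributed to this point. Between 2% and 5%, the loss due to score-2 entry is about 1 to 2 percentage points on either basis. Any further dilution of the hazard ratio, because these patients remain in the risk set, is not modelled.

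**The case against.** The strongest reply is that the trial recruits severe disease, so score 2 will hardly occur, and that ICU discharge covers many patients anyway. Much of this stands. Nine of the ten pairs include ventilation or a measured oxygenation deficit, and a score-2 entrant who is in the ICU can still have the event. The gap is confined to score-2 entrants who stay on the ward, and no bias between arms is shown, since eligibility precedes randomisation. The reply does not remove the gap: pair 2+5 remains open, and no text in the SAP sets a floor on the entry score.

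A reader might infer more than the SAP supports:

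- *That a patient saturating below 90% before oxygen is started enters at score 2.* Score 2 turns on not needing oxygen, not on not yet receiving it. Such a patient may well be scored 3. PaO2/FiO2 of 300 on room air likewise means a PaO2 of 63 mmHg (300 × 0.21).
- *That patients who met the criteria earlier and have since come off oxygen are knowingly admitted.* Two criteria carry a time window, but nothing says that past values suffice for the other three, which are ordinarily read as current. 5.5 records those same three measures at baseline.
- *That the problem would stay hidden.* A reduction cannot be computed without a starting score, so one has to be recorded. What is missing is its mention in 5.5 and its naming as the reference.
- *That ward recovery in general never counts.* A ward patient entering at score 3 can meet the two-point route.

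A further objection is that counting a one-point fall for some patients makes the endpoint depend on entry score. Stating the added event for everyone answers this in form: the definition is uniform and alters the result only where the floor prevents a two-point fall.

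**Conclusion.** The point holds in a limited form. The endpoint, scale and entry rule as written allow a patient to be randomised who can reach the primary event only by entering the ICU and leaving it alive. In such a patient full ward recovery is recorded as no improvement.

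The number affected is unknown and probably small. The effect on power is modest, about 1 to 2 percentage points at an assumed share of 2% to 5%, and would not by itself justify a change. The case rests on misclassified recovery and on a reference score that the definition leaves unnamed.

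The conclusion assumes that the reduction is measured from the score at randomisation. The power figures also assume exponential times at the SAP's medians and no events among score-2 ward entrants.

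**What to change.** In SAP 2.2.1 and 6.1.1, define the event as the earliest of:
- a two-point reduction from the ordinal score at randomisation,
- reaching score 1 (discharged alive, or discharge criteria met), or
- leaving the ICU alive.

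In 5.5, add the ordinal score at randomisation to the baseline variables.

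For anyone entering at score 3 or higher the added limb changes nothing, because reaching score 1 already is, or comes no earlier than, a two-point fall. The change costs only wording and should be made before outcomes are compared by arm. Its downside is that for a score-2 entrant a one-point fall counts as the event.

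No change to eligibility is needed for this repair. The entry rule in 5.2.1 and the scale in 2.2.1 do not fit together at score 2; whether to align them is for the sponsor to reconcile.

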5.2.2 Exclusion criteria

1. Patient/ family members who do not give consent to participate in the study.
2. Patients with age less than 18 years
3. Patients presenting with multi-organ failure
4. Pregnancy
5. Individuals with HIV and Viral Hepatitis and Cancer
6. Extremely moribund patients with an expected life expectancy of less than 24 hours
7. Hemodynamic instability requiring vasopressors
8. Previous history of allergy to plasma
9. Cirrhosis
10. Severe renal impairment with GFR < 30ml/min or recipients of RRT, peritoneal dialysis

11. Patients with uncontrolled diabetes mellitus, hypertension, arrhythmias and unstable Angina

5.3 Recruitment: Consort flow will include as per protocol-

Patients will be assessed for eligibility >>>randomization will be done for eligible participants >>> Allocation of treatment in two groups (one arm will be given convalescent plasma with standard medical treatment and another arm will be given standard medical treatment only) >>> follow up till 28 days.

5.4 Withdrawal/ Follow-up: Withdrawal is not expected, follow up till 28 days in all enrolled patient.

5.5 Baseline patient characteristics: following variables will be considered:

- Age at screening (years) = date of screening.
- Time from initial admission to randomization(days) = date of transfusion allotment by snooze method and transfusion of plasma.
- O₂ saturation at baseline.
- PiO₂/FiO₂ ratio at baseline.
- Respiratory rate at baseline.
- Need of Mechanical ventilation at baseline.
- SOFA score at baseline.
- For those who died: Date of death – transfusion start date or date of randomization.
- For those who are alive: Date of last follow-up – transfusion start date or date of randomization.

Section 6:

Analysis

6.1 Outcome definitions:

6.1.1 Definition of primary endpoint: Time to clinical improvement (Clinical improvement: Reduction of two points in ordinal scale or live discharge from the intensive care unit, whichever is earlier)

6.1.2 Secondary endpoints:

1. The proportion of patients in each category according to the ordinal scale at 48 hours and day 7, 14, and 28 after randomization
2. Duration of oxygen therapy
3. Duration of hospital stay
4. The proportion of patients on mechanical ventilation at day 7. (after randomization)
5. Mortality at day 7 and day 28 (after randomization)
6. Duration of Intensive Care Unit stay
7. Incidence of adverse effects in both groups
8. Presence of antibodies against SARS-CoV-2 in serum after plasma administration.
9. Cytokines and acute phase reactants

6.2 Analysis methods:

Continuous variables will be expressed as mean (SD) or median (range) and compared by Student's t-test or Mann-Whitney U test as appropriate. The categorical data will be analyzed using Chi-Square or Fisher's exact test. To compare pre and post values, a paired t-test or Wilcoxon signed-rank test will be used. To find out the predictor in survival analysis Cox-proportional hazard regression analysis will be applied. The actuarial probability of survival will be calculated by the Kaplan-Meier graph and compared by the log-rank test. The p value < 0.05 will be considered statistically significant.

6.3 Missing data: Not expected, if data are, we will try to impute.

6.4 Additional analyses: Not planned, if required an appropriate analysis will be carried out.

6.5 Harms: The risks will be the same as the risks related to the transfusion of Plasma Components, which are described below in the table. No additional risks of transfusing Convalescent plasma (CP) therapy are expected as a part of enrolment in this study as per previous literature available. The patient will be managed according to the standard of care at treatment centre. All the adverse transfusion events will be recorded and managed by clinicians or investigators as per standard treatment. Risk of Transfusion transmitted Infections (TTI) like transmission of HIV, Hepatitis B and Hepatitis C, Syphilis, and Malaria are very rare due to standard TTI testing of plasma donors at ILBS, New Delhi as per Drug and Cosmetics Act and Rules.

6.6 Statistical software: All statistical tests will be performed using SPSS for Windows version 22 (SPSS IBM Corp. Ltd. Armonk, NY).

6.7 Important references:

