3.3 Sample size: The sample size was calculated by assuming median survival in SMT as 24 days, and convalescent plasma with 18 days giving a reduction of 25% of the median time; then with $\alpha=5\%$ and $\beta=20\%$, we need to enrol 190 participants in each treatment arm by survival analysis method. $(Z_{1-\alpha/2}+z_{\beta})^2/((\ln(\theta))^2)$ where $Z_{1-\alpha/2}=1.96$ and $z_{\beta}=0.84$, $\theta=\lambda_1=\log 2/24$ $\lambda_0=\log 2/18$. Hence, we enrolled 400 cases which were equally and randomly allocated into two arms

3.3 Framework: it will be a comparative trial with the motive of testing the efficacy of convalescent plasma in severe COVID 19 patients with standard medical trial.

3.4 Treatment allocation:

Patients will be randomized to one of two groups by block randomization:

- **Group A:** Convalescent Plasma plus standard medical treatment
- **Group B:** Standard medical treatment only.

3.5 Statistical interim analysis and stopping guidance:

3.5.1 Statistical interim analysis:

Since it is of short duration trial no interim analysis is proposed.

3.5.2 Stopping guidance: No stopping rule is proposed until or unless ethical or IRB or designated government authority may ask for stopping the trial.

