3.5.3 Details of guidelines for stopping the trial early: Nil

3.5.4 Statistical analysis:

Continuous variables will be expressed as mean (SD) or median (range) and compared by Student's t-test or Mann-Whitney U test as appropriate. The categorical data will be analyzed using Chi-Square or Fisher's exact test. To compare pre and post values, a paired t-test or Wilcoxon signed-rank test will be used. To find out the predictor in survival analysis Cox-proportional hazard regression analysis will be applied. The actuarial probability of survival will be calculated by the Kaplan-Meier graph and compared by the log-rank test. The p value < 0.05 will be considered statistically significant.

3.5.5 Timing of final analysis: The final trial analysis will be performed once the trial is completed or the recruitment of patients ends or at the end of follow up (probably Jan 2021)

3.5.6 Timing of outcome assessments: Jan 2021.

Section 4: Statistical Principals:

4.1 Confidence intervals and P-values: The p value < 0.05 will be considered statistically significant.

Description and rationale for any adjustment for multiplicity:

No adjustments to the type I error will be made as there will be two groups.

Confidence intervals to be reported: Will be reported at 95%.

4.2 Adherence and Protocol deviations: No protocol deviation is expected and will adhere to the defined protocol of trial.

4.3 Analysis populations:

4.3.1 Definition of analysis populations:

Intention-to-treat (ITT) analysis of the sample/population of interest will be carried out in the severe COVID-19 infected individuals. There is no plan to do per-protocol (PP) population analysis as none will be allowed to switch to other treatment group.

4.3.2 ITT population:

This population includes all patients that will be randomized regardless of treatment adherence.

All summaries and analysis will be on the ITT population unless otherwise specified.

4.3.3 PP population:

Not applicable.

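### SAP 5.5 lets survival time start at transfusion or at randomisation, so the plasma arm can have a later time zero than controls, which can bias the comparison in either direction

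*SAP*

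**What the plan says.** Section 5.5, under baseline characteristics, holds the only derivation of an event time in the SAP. It has two lines, one for patients who died, which starts from the day of death, and one for survivors, which starts from the day they were last seen. Both subtract the same thing: "transfusion start date or date of randomization".

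Neither line says which date applies to which arm or patient. Group B receives "Standard medical treatment only" (3.4), so it has no transfusion date. Section 5.3 puts randomisation before treatment: "randomization will be done for eligible participants >>> Allocation of treatment in two groups". A transfusion can therefore fall on the day of randomisation or later, and only in Group A.

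Three other sections bear on the clock:

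- Section 4.3.2 defines the ITT set: "This population includes all patients that will be randomized regardless of treatment adherence". It is the default set for all analyses.
- Section 6.1.2 counts ordinal status, ventilation at day 7 and mortality from randomisation ("Mortality at day 7 and day 28 (after randomization").
- Sections 6.1.1 (primary endpoint) and 6.2 (Kaplan-Meier, log-rank, Cox) name no origin.

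**The concern.** A log-rank or Cox comparison is a randomised comparison only if both arms start the clock at the same point, and only randomisation is defined for everyone. Taken at its word, 5.5 permits plasma patients to be timed from transfusion and controls from randomisation. The days between randomisation and transfusion then leave one arm's follow-up and stay in the other's.

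A Group A patient who is never transfused has no transfusion-based time, and one with an event before transfusion has a negative one. The SAP does not say how either is handled. Because the trial is open-label, an unresolved choice between two dates would be settled by people who know the allocation. Day 28 mortality and the survival curve could also run on different clocks for the same patients.

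**Working it through.** **The plan's own figure.** Section 3.3 gives medians of 24 and 18 days, z-values of 1.96 and 0.84, and 190 per arm. (1.96 + 0.84)² / (ln(24/18))² = 7.84 / 0.08276 = 94.7, and twice that is 189.5, so 190 per arm. The figure is reproduced and is not affected by this point.

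**Inputs.** From the SAP: 200 per arm, 28 days of follow-up, control median 24 days. Assumed, because the SAP does not give them: a delay d from randomisation to transfusion of 1, 2 or 3 days; Day 28 mortality of 25% to 30%; the shape of the hazard. There is no true effect throughout, and the improvement calculations ignore death as a competing event.

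**Time to improvement, every patient kept, constant hazard.** Plasma patients still event-free at d are timed from transfusion; those with an earlier event are timed from randomisation. Plasma keeps all its events but loses d days of follow-up for each patient still at risk at d.

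- Hazard: λ = ln 2 / 24 = 0.02888 per day.
- Mean follow-up per patient to Day 28: (1 − exp(−28λ)) / λ = 0.5546 / 0.02888 = 19.20 days.
- Follow-up lost: d × exp(−dλ) = 0.97, 1.89 and 2.75 days.
- Apparent rate ratio: 19.20/18.23 = 1.05, 19.20/17.31 = 1.11, 19.20/16.45 = 1.17.

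Simulated log-rank trials agree, with hazard ratios of about 1.05, 1.10 to 1.11 and 1.16 to 1.17. A false significant plasma benefit appears in about 6%, 11 to 13% and 19 to 20% of trials, against a nominal 2.5%. If the improvement hazard rises over time (Weibull shape 1.5), the rates are about 7%, 16% and 32%.

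**Death, every patient kept.** The same arithmetic with 25% mortality:

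- λ = −ln(0.75) / 28 = 0.01027 per day; mean follow-up 0.25 / 0.01027 = 24.33 days.
- Follow-up lost: 0.99, 1.96 and 2.91 days.
- Apparent rate ratio: 24.33/23.34 = 1.04, 24.33/22.37 = 1.09, 24.33/21.42 = 1.14.

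Shorter plasma survival times look like harm. Across falling, constant and rising hazards the simulated hazard ratio is about 1.03 to 1.20, always against plasma.

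**Death, pre-transfusion deaths in Group A dropped.** The sign depends on the hazard:

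| Hazard over time | Apparent death hazard ratio, d = 1 to 3 days | Direction |
|---|---|---|
| Falling (Weibull shape 0.7, 25% mortality) | about 0.92 to 0.85 | for plasma |
| Constant | about 1.00 | none |
| Rising (Weibull shape 1.5, 30% mortality) | about 1.06 to 1.15 | against plasma |

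The constant-hazard result is exact in expectation: a constant hazard has no memory, so restarting the clock among survivors changes nothing. For improvement, dropping early Group A events likewise removes the bias at constant hazard; with a falling hazard it works against plasma.

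**One origin.** With randomisation as time zero in both arms, false plasma benefit occurs in about 2 to 4% of simulated trials, and the mean hazard ratio is 0.99 to 1.01.

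**The case against.** The best reply is that 5.5 is loose rather than wrong. The word *or* supplies randomisation as a fallback for anyone without a transfusion, 4.3.2 keeps all randomised patients, and the neighbouring line in 5.5 runs allotment and transfusion together, as if the dates were close. If transfusion always follows within hours, the bias is negligible.

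Much of this stands, and it rules out several stronger readings that a reader might infer:

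- **That the rule systematically favours plasma, as immortal time.** It does not. Group A patients can die while waiting, so that time is not guaranteed survival. For death with all patients kept, the bias is against plasma.
- **That early Group A deaths are deleted.** The SAP nowhere says so, and 4.3.2 points the other way. Deletion is only one way an analyst might handle a negative or undefined time.
- **That Day 28 mortality is understated.** Section 6.1.2 already counts that endpoint from randomisation.
- **That 5.5 defines the primary endpoint's clock.** Its two lines concern death and last follow-up. Carrying them to time to improvement is an inference, open only because 6.1.1 is silent.
- **That a 3-day delay is documented.** The only figure is that patients "will be transfused convalescent plasma within 3 days of symptom onset" (5.2.1). That window does not run from randomisation, and a 3-day delay after randomisation would use all of it.

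What the reply does not remove is the rule itself. A fallback for untransfused patients still leaves transfused patients on a later clock than controls.

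**Conclusion.** The point holds as an ambiguous time zero that can differ by arm and, if it does, contradicts 4.3.2 and 6.1.2. It is more than missing detail, because the SAP states a derivation and that derivation admits a biased analysis.

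The size rests on an unstated delay, and the sign rests on the endpoint, the handling of pre-transfusion events and the hazard shape. The largest exposure is the primary endpoint, if the same clock is used there: at 1 day the inflation is modest (about 6% against 2.5%), and at 3 days it is serious (about 19%). For death, the reading most consistent with ITT disadvantages plasma. An apparent survival benefit needs both dropped pre-transfusion deaths and a falling hazard. No claim of a built-in advantage for plasma is supported.

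**What to change.** - In 5.5, strike the transfusion-start alternative from both lines, so that time is the date of death or last follow-up minus the date of randomisation in both arms.
- In 6.1.1, define the primary endpoint as time from randomisation to clinical improvement.
- State that Group A patients who are never transfused, or who have an event before transfusion, stay in Group A on that clock.
- Report days from randomisation to transfusion in Group A as a description only.

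The cost is a wording change. Every ITT patient has a randomisation date by definition, so no new data are needed, and the sample size and clinical conduct are unaffected.

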1.5 SAP revisions: No

1.6 Roles and responsibility:

1.6.1.1 [name] [name]: Chief Coordinator/Clinical Lead

1.6.1.2 [name]: Chief investigator/principal investigator

1.6.1.3 [name]: Senior Statistician

1.6.1.4 [name]: Clinical Trial Coordinator.

1.6.1.5 [name]: Wrote the SAP

SECTION 2

INTRODUCTION:

2.1 Background and rationale:

The outbreak of SARS-CoV2 infection, which had originated in Wuhan, China, has become a pandemic involving more than 10 million people across the globe with almost half million deaths and still counting (1). The case-fatality rate of COVID-19 has ranged from 1.2-13% (1,

2). The current evidence-based strategy relies on providing supportive care in mild to moderate cases and providing mechanical ventilation and extracorporeal membrane oxygenation in severe cases. There is no targeted drug therapy available at present. Some studies have indicated benefits with, intravenous Remdesivir and Dexamethasone in reducing the duration and severity of illness, but not mortality (3-5). Apart from antiviral drugs, virus-specific neutralizing antibodies, which could accelerate virus clearance and prevent entry into target cells, could serve as a mechanism for the restriction and clearance of the viruses by the host. The plasma of convalescent patients who have recovered from SARS-CoV2 infection may contain such neutralizing antibodies which may accelerate virus clearance in an infected recipient and be used in the treatment of patients with COVID-19 (6). The experience of using convalescent plasma is derived from its utility in improving the survival rate of patients with SARS infection wherein the patients who had no response to intravenous corticosteroids showed improvement. Providing passive antibody therapy by convalescent plasma in COVID-19 infection could be one of the approaches towards disease mitigation in the absence of definitive treatment (5, 6). This approach can be effective in patients before they develop a humoral response to COVID-19.

2.2 Objectives:

2.2.1 Primary objective:

Efficacy of convalescent plasma in severe COVID 19 patients in time to clinical improvement (Clinical improvement: Reduction of two points in ordinal scale or live discharge from the intensive care unit, whichever is earlier) [Time Frame: Day 28]

The six-point scale is as follows:

- a. death=6;
- b. hospital admission for extracorporeal membrane oxygenation or mechanical ventilation=5;

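### The primary endpoint credits any live ICU discharge and is not anchored to the score at randomisation, so a patient who worsens and returns to the ward no better than at entry can count as improved

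*SAP*

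**What the plan says.** The primary objective (SAP 2.2.1) is "Efficacy of convalescent plasma in severe COVID 19 patients in time to clinical improvement", with a Day 28 time frame. Sections 2.2.1 and 6.1.1 both define improvement as "Reduction of two points in ordinal scale or live discharge from the intensive care unit, whichever is earlier". Neither section says from which score the two points are counted, and neither attaches a condition to the ICU route.

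The six-point scale in 2.2.1 grades respiratory support and discharge, not place of care. Score 3, for example, is "hospital admission for oxygen therapy (but not requiring high-flow or non-invasive ventilation) =3".

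Entry (5.2.1) requires confirmed severe disease, "meeting any 2 of the following criteria". Ventilation is one of five options. The other four are physiological or radiological, such as "Oxygen saturation level less than 90 % in resting state". Neither the inclusion list nor the exclusions in 5.2.2 mention place of care.

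The baseline variables in 5.5 include "Need of Mechanical ventilation at baseline", so some patients are expected not to be ventilated. ICU status at baseline is not listed. Section 6.4 plans no additional analyses.

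**The concern.** A composite of this kind works as intended when every patient starts in ICU, because leaving ICU alive is then a step forward from the starting point. For a patient who starts elsewhere, the ICU route is closed until that patient is admitted to ICU, which will usually mean getting worse. Returning to the ward then registers as improvement even if the patient is no better than at randomisation, or is worse.

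This is the only primary endpoint, so the rule decides who counts as an event and when. If late ICU admission differs between arms, these events differ too, and the comparison shifts for reasons unrelated to net improvement. Nothing planned would reveal this in the primary result: the two components are not to be reported separately, and no sensitivity analysis on the two-point route is planned.

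**Working it through.** **Paths under the literal wording.** Take a patient randomised outside ICU at score 3.

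| Course | Net change from entry | Two-point fall from entry score | Two-point fall from worst score | ICU route | Scored |
|---|---|---|---|---|---|
| 3 → 1, never in ICU | −2 | yes | yes | closed | success |
| 3 → 2, never in ICU | −1 | no | no | closed | not a success |
| 3 → 4 in ICU → 3 on ward | 0 | no | no | met | success |
| 3 → 5 in ICU → 3 on ward | 0 | no | yes | met | success |
| 3 → 5 in ICU → 4 on ward | +1 | no | no | met | success |

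The second and third rows show the problem: a patient who gains a point without worsening does not count, while one who worsens and only regains the starting score does. The fourth row shows that restricting the ICU route alone is not enough. With no reference score stated, 3 → 5 → 3 can still be read as a two-point reduction.

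**The plan's own figure.** SAP 3.3 gives 190 per arm from medians of 24 and 18 days, with 1.96 and 0.84 as the normal quantiles:

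2 × (1.96 + 0.84)² / [ln(24/18)]² = 15.68 / 0.08276 = 189.5, rounded to 190.

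The figure reproduces and does not bear on this point. It is used only to confirm that the medians are read as intended.

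**Expected events by Day 28.** Inputs: medians of 24 and 18 days and 400 patients in two equal arms (SAP 3.3), and 28 days of follow-up (SAP 5.4). Exponential times are assumed and deaths are ignored.

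- Control: 1 − 2^(−28/24) = 0.555
- Plasma: 1 − 2^(−28/18) = 0.660
- Total: 200 × (0.555 + 0.660) = 243

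**Patients on the problem path.** The SAP gives none of the fractions needed, so all of these are assumptions. Let f be the share outside ICU at randomisation, g the share of those who later enter ICU, and h the share of those who leave ICU alive by Day 28.

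- All start in ICU (f = 0): 0 patients
- f = 0.30, g = 0.10, h = 0.50: 400 × 0.30 × 0.10 × 0.50 = 6, and 6/243 = 2.5%
- f = 0.60, g = 0.20, h = 0.60: 400 × 0.60 × 0.20 × 0.60 = 28.8, and 28.8/243 = 11.9%

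For any given fractions these counts are upper bounds on successes created by the rule. Some of these patients would reach score 1 by Day 28 anyway, and for them ICU exit only brings the event date forward. The fractions themselves are loose. With 10% to 50% outside ICU, and 5% to 20% of those entering ICU and leaving alive, the count is 200 × 0.10 × 0.05 = 1 to 200 × 0.50 × 0.20 = 20 per arm.

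**Direction.** Let half of each arm start outside ICU. Suppose 20% of those in one arm and 10% in the other enter ICU and leave alive. The first arm then has 200 × 0.5 × 0.20 = 20 such events and the second 200 × 0.5 × 0.10 = 10. The extra 10 favour plasma if plasma is the arm with more ICU transfers, and count against it if control is. The SAP gives no basis for choosing between the two.

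**The case against.** The strongest objection is that the problem needs patients outside ICU at randomisation, and the SAP never says that such patients are enrolled. It only omits ICU from the criteria. The protocol, not at hand, may fix the place of care. Several features fit an ICU population: ICU discharge in the primary endpoint, ICU stay as a secondary endpoint, SOFA at baseline, and a requirement for two severity criteria. This stands as a limit on size, and zero belongs in the range. It does not clear the wording. Section 1.1 says the SAP sets out the inclusion and exclusion details, and the criteria it gives admit patients anywhere in the hospital.

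A reader might go further and infer that the endpoint would turn harm from plasma into apparent benefit, for example through transfusion reactions leading to ICU transfer. The documents do not support that. They give no rate for such transfers, section 6.5 expects no risk beyond that of ordinary plasma components, and the opposite imbalance is equally possible. The percentages above also pool both arms, so they measure misclassification and not bias in the treatment comparison.

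Some deterioration would show elsewhere: ordinal categories at 48 hours and Days 7, 14 and 28, ventilation at Day 7, mortality, ICU stay and adverse effects are all secondary endpoints. They help interpretation but do not repair the primary definition.

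The trial is open-label ("It will be a open-labeled; phase III randomized controlled trial"), and ICU discharge involves judgement. That is a separate matter, which would apply equally if every patient began in ICU.

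**Conclusion.** The point holds as a defect in a stated rule. Applied literally, sections 2.2.1 and 6.1.1 score some patients with no net gain, or a net loss, as primary successes, and the eligibility criteria in 5.2 do not rule such patients out. The lack of a reference score affects the two-point route as well as the ICU route.

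The size cannot be derived from the SAP. It is zero if all patients are in ICU at randomisation and at most about 29 of roughly 243 events (about 12%) at the top of the first set of assumed fractions. Other fractions give other bounds. The 243 rests on exponential times with the planned medians and ignores deaths. The direction of any bias is unknown: the rule favours plasma if plasma leads to more ICU transfers and dilutes a real benefit if plasma prevents them. The wording should be corrected before analysis, but the documents do not show that the result is biased.

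**What to change.** Amend 2.2.1 and 6.1.1 together:

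- Define the two-point reduction relative to the score at randomisation.
- Count ICU discharge only for patients in ICU at randomisation, and only if the score on that day is no higher than at randomisation.
- Add ICU status at randomisation to the baseline list in 5.5, and record the score on the day of ICU discharge.
- Prespecify a sensitivity analysis using only the baseline-anchored two-point reduction.
- Report by arm how many events came from each component.

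If the sponsor keeps the composite as it stands, the last two items are the minimum.

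The cost is SAP wording, one further analysis, and two data items to confirm or add. Both may already be available: ICU dates are needed for the ICU-stay endpoint, and time to a two-point reduction needs dated scores, although 6.1.2 lists fixed assessment times only. There will be slightly fewer events. The change must be dated before outcome data are examined.
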